- Blood work for pharmacodynamics, vaccine related antibodies, LINE-1, serum antibody testing, and peripheral blood mononuclear cells (PBMCs) prior to vaccine and investigational product administration and 2, 4 and 6 hours post administration
- SAVE procedures (if applicable)

After the observation period (6 hours) and prior to discharge from the Clinical Research and Trials Unit, a reassessment of vital signs including orthostatic blood pressures will be conducted on all study participants.

6.3 Visit 3, Safety Follow-up –Day 1

This visit will be recorded as “Day 1” and will require a visit to the research center where the following tests will be performed:

- Brief physical examination
- Vital signs (orthostatic blood pressure, oxygen saturation, temperature, respiratory rate, weight, and heart rate)
- Review of medications
- Review of adverse events
- Respiratory infection assessment
- Quality of Life (QoL) questionnaire
- ECG
- Blood work – labs [serum chemistry, Hematology, coagulation, cytokines, LINE-1, and vaccine related antibodies]
- Urine collection for urinalysis

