6.4 Visit 4, Safety Follow-up –Day 7 (remote visit)

This visit will be recorded as “Day 7” and will be a remote visit where the following tests will be performed:

- Review of medications
- Review of adverse events
- Respiratory infection assessment
- Quality of Life (QoL) questionnaire

6.5 Visit 5, Follow-up - Month 1

This visit will be recorded as “Month 1” and will require a visit to the research center where the following tests will be performed:

- Vital signs (orthostatic blood pressure, oxygen saturation temperature, respiratory rate, weight, and heart rate)
- Review of medications
- Review of adverse events
- Respiratory infection assessment
- Quality of Life (QoL) questionnaire
- ECG
- Blood work – labs [serum chemistry, Hematology, coagulation, CMV, cytokines, vaccine related antibodies, LINE-1, peripheral blood mononuclear cells (PBMCs) and biomarkers of senescence]
- Urine collection for urinalysis

6.6 Visit 6, Follow-up – Month 2

This visit will be recorded as “Month 2” and will require a visit to the research center where the following tests will be performed:

- Vital signs (orthostatic blood pressure, oxygen saturation temperature, respiratory rate, weight, and heart rate)
- Review of medications
- Review of adverse events
- Respiratory infection assessment
- Quality of Life (QoL) questionnaire
- ECG
- Blood work – labs [serum chemistry, Hematology, coagulation, cytokines, vaccine related antibodies, LINE-1, and peripheral blood mononuclear cells (PBMCs)]
- Urine collection for urinalysis
- Frailty Assessments (includes questionnaires, physical function testing and body composition)

6.7 Visit 7, Follow-up – Month 6

This visit will be recorded as “Month 6” and will require a visit to the research center where the following tests will be performed:

- Vital signs (orthostatic blood pressure, oxygen saturation temperature, respiratory rate, weight, and heart rate)
- Review of medications
- Review of adverse events
- Respiratory infection assessment
- Quality of Life (QoL) questionnaire
- ECG
- Blood work – labs [serum chemistry, Hematology, coagulation, CMV, cytokines, LINE-1, and vaccine related antibodies]
- Urine collection for urinalysis
- Frailty Assessments (includes questionnaires, physical function testing and body composition)

6.8 Visit 8, Follow-up – Month 12

This visit will be recorded as “Month 12” and will require a visit to the research center where the following tests will be performed:

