6.15 Adverse Events

Adverse event monitoring will be conducted throughout the study for all subjects. The AE and serious adverse event (SAE) reporting period begins at the time of informed consent and continues through study completion. Adverse events will be assessed at every site and remote visit.

The Investigator will follow-up on all AEs observed or reported by the subject up to the end of the reporting period or until follow-up is no longer necessary. The Investigator will follow-up on SAEs until they are considered resolved or the outcome is known.

Definitions, documentation, and reporting of AEs are described in Section 8. Serious adverse events must be reported within 24 hours as described in Section 8.2.

Table S-1. Schedule of Events

PERIOD	Screening Visit	Treatment Visit	Safety Follow-Up		Monthly Follow-Up					
ON-SITE VISIT	1	2	3	4 (remote)	5	6	-	7	-	8
WEEK	-4	0	Day 1	1						
MONTH					1	2	3 to 5 ^[p]	6	7 to 11 ^[p]	12
Visit Window, week(s)	-28 days			± 1 day	± 1 week					
General Eligibility, Safety, and Frailty Assessments										
Eligibility assessment	X									
Written informed consent	X									
MMSE cognitive status assessment	X									
Frailty assessments ^[a]	X						X	X		X
Brief physical examination ^[b]	X		X							
Medical history	X									
Demographic Information	X									
Vital signs/oxygen saturation/Ht/Wt ^[c]	X ^[q]	X ^{[d][q]}	X ^[q]		X ^[q]	X ^[q]		X ^[q]		X ^[q]
12-lead ECG	X		X		X	X		X		X
AE assessment, including respiratory infection assessment	X	X	X	X	X	X	X	X	X	X
Concomitant medications	X	X	X	X	X	X	X	X	X	X
Quality of life (QoL) questionnaire	X		X	X	X	X	X	X	X	X
Study Drug Administration										
Study drug		X								
Laboratory Assessments										
Serum chemistry ^[e]	X		X		X	X		X		X
Hematology ^[f]	X		X		X	X		X		X
Coagulation ^[g]	X		X		X	X		X		X
Serum virology ^[h]	X									
Urinalysis ^[i]	X		X		X	X		X		X
Serum for entolimod-reactive antibodies ^[j]	X		X		X	X		X		X
Plasma for pharmacodynamics ^[k]		X								
Serum for vaccine related antibodies ^[l]		X			X	X		X		X
Peripheral blood mononuclear cells (PBMC) ^[m]		X			X	X				X
COVID-19, PCR [SARS Coronavirus 2, Molecular Detection, PCR (NP)]		X								X
Exploratory Procedures										
SAVE ^[n]		X								
Biomarkers of senescence ^[o]		X			X			X		X
SARS-CoV-2 IgG Ab [SARS Coronavirus 2 IgG Ab, Serum]		X								X

Footnotes
[a] To be collected at screening, baseline, months 2, 6 and 12 (includes questionnaires, physical function testing, and body composition)

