The distribution of antibody titers (A/H1N1, A/H3N2, B) during follow up is anticipated to be skewed based on reporting in prior studies and a log-transformation will be applied to these outcomes. Antibody titers are measured at multiple time points in the first week after treatment, 4 weeks, 2 months, 6 months, and 12 months. A hierarchical mixed-effects regression model will be fit separately for the 3 endpoints, adjusting for the baseline/screening observation of the titer (an analysis of covariance (ANCOVA) approach). The model will include random subject-specific intercepts and model time as discrete. The primary outcome comparison is a contrast analysis of the outcome at 4 weeks comparing each entolimod dose to placebo. As the overall aim of this study is to assess safety and identify potential efficacy of entolimod, especially the dose most likely to succeed in Phase III study, we apply a one-sided test at alpha level 0.15 to each dose comparison (vs. placebo) and antibody titer combination, without multiplicity adjustment. The primary analysis will be conducted using the modified intent-to-treat analysis dataset.

Secondary Hypotheses: Secondary and exploratory endpoints require a variety of standard statistical methods.

Key secondary endpoints include the frailty indices, measures of physical function (6 minute walk test and grip strength), and quality of life (QOL). Frailty indices are measured at 2, 6, and 12 months and QOL measured at each study visit. For these outcomes, linear mixed effects models will assess the relationship between randomized arm and outcomes over time. Discrete times will be considered corresponding to the study visit and secondary analyses may consider continuous linear time (constant slope over time) for changes in the outcome. For these outcomes, the 12 month observation is the primary comparison.

Upper respiratory infections, including influenza, will be recorded over the follow up period. We anticipate the total number of these will be infrequent. Thus, we compare the outcome of any infection (vs. no infection) across randomized arms using a Pearson chi-square test or Fisher's exact test. Secondary approaches may consider analysis of the ordinal count of the number of infections, analyzed using a trend test.

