Cellular immune response and pharmacodynamics parameters, including concentration of circulating plasma cytokines and cytokine response to viral stimulation are outcomes compared using analysis of variance (ANOVA) methods across the four comparison groups. Pharmacodynamic measures will be listed and will be summarized using appropriate graphical and tabular methods. Statistical analysis evaluating pharmacodynamic parameters will be performed using contrasts in the context of analysis of covariance (ANCOVA).

Handling of Missing Data

In the analysis of primary outcomes, data are analyzed using a hierarchical regression approach assuming missing data are missing at random. In a secondary approach, patients with dropout or missing follow up due to influenza viral infection during follow up will be assumed missing not at random and missing data will be imputed to the baseline/screening value reflecting no increase

from baseline in antibody titers among these patients. Dropout for other causes will be considered similarly, except death unrelated to influenza, which will continue to be assumed as missing at random.

Interim Analysis

No interim analysis will be performed for efficacy assessment.

Multiplicity

No adjustments will be made for multiplicity correction to dose comparisons or the primary endpoints as the study aim is to identify promising doses for subsequent phase III study. Secondary outcomes will also not be adjusted for multiple comparisons.

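### The primary titer model names only a random intercept, so on a plain reading the 4-week test uses a variance pooled over visits and its 15% level is not secured

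*Combined protocol and SAP*

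**What the plan says.** Section 7.2 fits one mixed model to each log titer, adjusts for the baseline value, and tests each dose against placebo at 4 weeks, one-sided at 0.15, without multiplicity adjustment. On covariance it says only: "The model will include random subject-specific intercepts and model time as discrete". The Study Summary mentions linear mixed effects models and nothing more. The missing-data paragraph adds: "In the analysis of primary outcomes, data are analyzed using a hierarchical regression approach assuming missing data are missing at random".

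The visits that enter the model are described in different ways:

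- Section 7.2: "Antibody titers are measured at multiple time points in the first week after treatment, 4 weeks, 2 months, 6 months, and 12 months".
- Section 6.2 (treatment visit): "Blood work for pharmacodynamics, vaccine related antibodies, LINE-1, serum antibody testing", in a bullet timed before dosing and at 2, 4 and 6 hours after.
- Section 6.3 (Day 1): "coagulation, cytokines, LINE-1, and vaccine related antibodies".
- Section 6.4 (Day 7): this "will be a remote visit where the following tests will be performed", and no blood draw is listed.
- Table S-1: the row "Serum for vaccine related antibodies" is marked only at the treatment visit and months 1, 2, 6 and 12. Its footnotes attach the 2, 4 and 6 hour draws to G-CSF and IL-6, not to HAI titers.

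Section 6.11 defers to the schedule of events, so Table S-1 is the more likely schedule.

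**The concern.** A model whose only random term is a subject intercept, with nothing further said about the residuals, gives every visit the same total variance. The 4-week contrast is then judged against a variance averaged over visits up to a year after vaccination, and possibly over visits within hours of it. If titers given baseline vary more at 4 weeks than on average, the standard error is too small and the test exceeds 15%. If they vary less, the test is conservative and loses power.

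These contrasts are the primary immunogenicity test. The plan waives multiplicity adjustment "as the study aim is to identify promising doses for subsequent phase III study", so the 15% per-comparison level is the only error control stated for them. Under the plan as written, that level depends on a variance pattern nobody has specified and on a visit list that the document gives in more than one form.

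**Working it through.** **Inputs from the documents.** 25 per arm, one-sided alpha 0.15, CV 2.0 for A/H1N1 and 1.4 for A/H3N2 and B (section 7.1); outcome visits at months 1, 2, 6 and 12 (Table S-1).

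**Assumed, because the documents do not give them.** Baseline log SD 1.0, baseline slope 0.6 at late visits, correlation 0.8 between late visits, early titers equal to baseline plus assay error of SD 0.25, and the SD paths below (SDs given baseline, relative to month 1).

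**Step 1: log SD at 4 weeks.** √ln(1 + 2.0²) = 1.269 and √ln(1 + 1.4²) = 1.042. With these SDs an unadjusted one-sided t-test has power 81.2% (doubling) and 82.8% (80% increase), not the 90% in section 7.1. That is a separate point and does not affect the level. The power figures in step 5 include baseline adjustment under the assumed values.

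**Step 2: standard error.** With complete data and arm-by-visit means (needed for a 4-week contrast), the REML total variance of a random-intercept model is essentially the mean of the visit variances, V̄. The model SE is about √(2V̄/25); the true SE is about √(2V₄/25), where V₄ is the 4-week variance given baseline. With R = V̄/V₄ the SE is off by a factor √R, so

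level = 1 − Φ(1.036 × √R).

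At R = 1 this returns the plan's 15.0%.

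**Step 3: Table S-1 visits (main case).** Simulated levels come from 20,000 trials with three dose contrasts each.

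| SD path, months 1, 2, 6, 12 | R | Formula | Simulated, CV 2.0 / 1.4 |
|---|---|---|---|
| constant | 1 | 15.0% | 15.0 / 15.3% |
| 1, 0.95, 0.85, 0.75 (mild fall) | (1 + 0.9025 + 0.7225 + 0.5625)/4 = 0.797 | 17.7% | 17.9 / 17.9% |
| 1, 0.9, 0.7, 0.5 (strong fall) | (1 + 0.81 + 0.49 + 0.25)/4 = 0.638 | 20.4% | 20.7 / 20.2% |
| 1, 1.05, 1.15, 1.25 (mild rise) | (1 + 1.1025 + 1.3225 + 1.5625)/4 = 1.247 | 12.4% | 12.8 / 12.4% |
| 1, 1.1, 1.3, 1.5 (strong rise) | (1 + 1.21 + 1.69 + 2.25)/4 = 1.538 | 9.9% | 10.0 / 10.2% |
| variances 1, 0.8, 1.2, 1 | 1 | 15.0% | 14.9 / 15.1% |

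The last row shows that what matters is the average relative to 4 weeks, not inequality as such. A 4-week ANCOVA stayed at 14.7–15.4% throughout. The chance that at least one of three ineffective doses passes for one strain was 31% (constant), 39–40% (strong fall) and 22% (strong rise).

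A separate run with other paths agreed. SDs 1, 1, 0.8, 0.7 give R = 0.7825, formula 18.0%, simulated 17.3%. SDs 1, 1.1, 1.2, 1.3 give R = 1.335, formula 11.6%, simulated 12.0%.

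**Step 4: if early titers entered.** Section 3.6 says titers are generated weeks after vaccination, so early values would sit near baseline. Take an assumed early relative SD of 0.3 and equal variance from month 1:

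- Day 1 only: R = (4 + 0.09)/5 = 0.818, level 17.4%.
- Day 1 and three same-day draws: R = (4 + 4 × 0.09)/8 = 0.545, level 22.2%.

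Across the SD paths, with the step-3 simulation inputs, the simulated ranges were 12.3–22.3% and 17.4–26.7%. As a software check, SDs 1, 1, 0.8, 0.7 with Day 1 at 0.3 give R = 0.644 and formula 20.3%. REML fits rejected in 24% of 300 and 21.1% of 1,200 trials, together 325/1,500 = 21.7% (Monte Carlo SE about 1.1 points).

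**Step 5: missing data.** Table S-1 visits, 10% missing the 4-week visit at random, about 5% dropping out before each later visit (more often after a low titer), 8,000 trials per scenario:

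| | Random intercept | Unstructured, Kenward-Roger |
|---|---|---|
| Level: constant / strong fall / strong rise | 15.1 / 20.1 / 10.4% | 15.1–15.2% in all |
| Power, doubling, CV 2.0 | 86.6% constant, 80.7% strong rise | 86.4% |
| Power, 80% increase, CV 1.4 | 91.0% constant, 86.5% strong rise | 90.8% |

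ANCOVA of the observed 4-week titers had level 15.2% and power 84.6% and 89.2%. Mean estimates matched the true effect to 0.001 for all three methods.

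**The case against.** The strongest reply is that this is silence, not a stated error. Section 7.2 never says that one variance applies to all visits, and a random intercept can be combined with visit-specific residual variances or robust standard errors. That is true. But the text names neither, and a random intercept adds nothing to an unstructured covariance, so naming it points away from that model.

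Second, no magnitude comes from the documents. This stands. With equal variances the level is 15% whichever visits enter, and the mild paths move it only 2 to 3 points. The strong paths are wide bounds. At CV 2.0 the 4-week variance given baseline is 1.610 − 0.36 = 1.25. The strong rise then implies a month-12 log variance of 2.25 × 1.25 + 0.36 = 3.17, a CV near 4.8. The strong fall implies 0.25 × 1.25 + 0.36 = 0.67, an SD of 0.82, below the assumed baseline SD of 1.0.

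Third, the early-titer figures depend on a schedule that Table S-1 contradicts. This stands too, and they are not the expected case. Likewise, the negative correlation between baseline and 6-week change in the Td study (section 1.4.2.4) is what any single slope below 1 produces. It argues against a common baseline slope only if near-baseline early titers are modelled alongside late ones.

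Fourth, with complete data and equal arms the three dose contrasts have nearly the same standard error, so pooling does not reorder the doses, and the plan gives no numeric selection rule. Correct; what is exposed is whether a dose passes the 15% test, not its rank.

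Finally, the missing-data simulation drops the 4-week visit completely at random. It therefore shows a gain in power over ANCOVA, not in bias.

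**Conclusion.** The concern holds. Under the plain reading of section 7.2, the one-sided 15% level of the primary contrasts is guaranteed only if the 4-week variance given baseline equals the average over the modelled visits. With Table S-1 visits, plausible mild departures put the true level at about 12–18%, and the wide bounds at about 10–21%. Larger inflation would need early titers in the model. Direction and size cannot be known beforehand, since no variance by visit is given, and every figure other than the plan's 15% rests on assumed SD paths. With complete data the estimate and the ordering of doses are essentially untouched; the standard error, and hence the level or the power, is what is at risk. This should be changed before analysis: it is cheap, and a model with visit-specific variances held the level in every scenario examined.

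**What to change.** Keep a likelihood-based mixed model as primary, so that the missing-at-random handling is preserved, and specify:

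- post-baseline outcome visits from 4 weeks onward (months 1, 2, 6 and 12), with any earlier titers summarised descriptively;
- arm-by-visit and baseline-by-visit terms;
- an unstructured covariance with Kenward-Roger degrees of freedom;
- a fallback for non-convergence that still lets the variance differ by visit, such as heterogeneous Toeplitz;
- a 4-week ANCOVA as a sensitivity analysis (it equals this model only with complete data).

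Reconcile the titer sampling times in sections 6.2, 6.3 and 7.2 with Table S-1.

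The cost is wording and no new data. The covariance has 10 parameters (4 × 5/2) instead of 2, which cost 0.2 points of power in the simulation when variances were in fact equal (86.4% against 86.6%; 90.8% against 91.0%). The standard error may come out larger than under pooling; where it does, the larger value is the correct one.

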3.5 Secondary Study Endpoints

Pharmacodynamics and Cellular Immune Responses to Influenza Vaccination

- Time to onset and the number of upper-respiratory infections, including (but not limited to) influenza viral infections (as indicated by subject self-reporting)
- Changes in the concentration of circulating plasma cytokines including (but not limited to): IL-6 and G-CSF as pharmacodynamic indicators of entolimod's activity (measured using MSD assay platform)
- Changes to 10 cytokine/chemokine mediators of adaptive immune function (IFN- γ , IL-1 β , IL-2, IL-4, IL-6, IL-8, IL-10, IL-12p70, IL-13 and TNF- α) in PBMC culture supernatants at 0 and 24 hours after influenza (A/H1N1, A/H3N2 and B) viral stimulation as detected by Meso Scale Discovery, V-PLEX Proinflammatory panel human immunoassay kits.
- Changes in the quantification of IFN γ -positive cells as a marker of cell-mediated immunity (CMI) after vaccination using influenza virus-specific IFN- γ ELISPOT assay kits from R&D Systems.

- Changes in frailty indices and quality of life (QoL) of individuals receiving entolimod versus placebo
- Changes in measures of physical function (6-minute walk test, grip strength) and body composition

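### Section 7.2 names no baseline term in the frailty, physical function and quality-of-life models, although screening values are collected and adjusting for them would gain precision at no cost

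*Combined protocol and SAP*

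**What the plan says.** Section 7.2 of the combined protocol and SAP, under Secondary Hypotheses, treats frailty indices, the 6-minute walk test, grip strength and quality of life as key secondary endpoints. For them, "linear mixed effects models will assess the relationship between randomized arm and outcomes over time". Visits are modelled as discrete times. On timing it says: "Frailty indices are measured at 2, 6, and 12 months and QOL measured at each study visit". On the main contrast: "For these outcomes, the 12 month observation is the primary comparison". Change is mentioned only in an optional further analysis: "secondary analyses may consider continuous linear time (constant slope over time) for changes in the outcome".

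The same section handles the primary titers differently, with a mixed model "adjusting for the baseline/screening observation of the titer", which it labels ANCOVA. It also specifies ANCOVA contrasts for the pharmacodynamic parameters. Section 7.1 expects the baseline-adjusted titer analysis to have more power than the unadjusted t-test used for sizing.

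Section 3.5 defines the secondary endpoint as "Changes in frailty indices and quality of life (QoL) of individuals receiving entolimod versus placebo", and words physical function as changes too. Section 6.1 lists the quality-of-life questionnaire and the frailty assessments, including physical function testing, at the screening visit. The footnote to Table S-1 on frailty confirms collection at screening.

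**The concern.** The trial collects a pre-dose value of each of these outcomes and defines the endpoints as changes. It also relies on baseline adjustment elsewhere. The sentence that sets the model for these outcomes mentions only arm and time. Read literally, the month-12 comparison is of post-treatment levels.

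With 25 subjects per arm, precision is scarce. Section 1.5 hypothesizes that entolimod may delay or alleviate aspects of frailty, and these are the endpoints that address it. Leaving out a correlated baseline widens the intervals and leaves chance imbalance uncorrected. Leaving its role unstated also keeps several analyses open, with different precision and possibly different answers, to be chosen after the data are seen.

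**Working it through.** The documents state no power, detectable difference, SD, test level or baseline correlation for these endpoints, so there is no plan figure to reproduce.

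**Inputs.** From the documents: 25 per arm (section 7.1), month 12 as the main comparison (section 7.2). Assumed: baseline-to-month-12 correlation r from 0.3 to 0.8, equal SD (σ) at baseline and month 12, complete data.

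**Variance of one dose-versus-placebo contrast at month 12.**

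- Levels without baseline: 2σ²/n = 2σ²/25 = 0.080σ².
- Change from baseline: 2σ² × 2(1 − r)/n.
- Screening value as covariate: 2σ²(1 − r²)/n. At r = 0.5 this is 0.080 × 0.75 = 0.060σ²; at r = 0.7 it is 0.080 × 0.51 = 0.041σ².

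The saving against levels is therefore r². The saving against a change score is 1 − (1 − r²)/[2(1 − r)] = (1 − r)/2.

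| r (assumed) | Change score, relative to levels | ANCOVA, relative to levels | Saved vs levels | Saved vs change score |
|---|---|---|---|---|
| 0.3 | 1.40 | 0.91 | 9% | 35% |
| 0.5 | 1.00 | 0.75 | 25% | 25% |
| 0.6 | 0.80 | 0.64 | 36% | 20% |
| 0.7 | 0.60 | 0.51 | 49% | 15% |
| 0.8 | 0.40 | 0.36 | 64% | 10% |

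Estimating the covariate slope costs little. With two arms of 25, the ANCOVA variance is inflated by about 1 + 1/46, so the savings against levels at r = 0.5, 0.6 and 0.7 become 23%, 35% and 48%.

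**Does the mixed model recover this by itself?** An exact generalized least squares check (four arms of 25; visits at 0, 2, 6 and 12 months; compound symmetry; complete data) gives these relative variances of the month-12 contrast at r = 0.5, 0.6 and 0.7:

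- Random intercept, post-dose visits only: 1.00, 1.00, 1.00.
- Screening added as an unconstrained response, month-12 level contrast: 1.00, 1.00, 1.00.
- The same model, change-from-screening contrast: 1.00, 0.80, 0.60.
- Screening as a response with a common mean across arms: 0.75, 0.64, 0.51, the same as ANCOVA.

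A random intercept alone does not do the work of a baseline covariate.

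**Illustrative power.** Assume a true difference of 0.6 SD, 25 per arm and no dropout. Noncentral t, 48 degrees of freedom, noncentrality [0.6/√(1 − r²)] × √(25/2). For r = 0 (no adjustment) this is 0.6 × 3.536 = 2.12; for r = 0.5 it is 0.693 × 3.536 = 2.45.

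| Test level | Unadjusted | r = 0.5 | r = 0.6 | r = 0.7 |
|---|---|---|---|---|
| Two-sided 0.05 (assumed) | 55% | 67% | 74% | 83% |
| One-sided 0.15 (the titer test level) | 86% | 92% | 95% | 97% |

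**Size of chance imbalance.** The difference in mean baseline between two arms of 25 has a standard error of √(2/25) = 0.28 SD. About 29% of such comparisons will differ by more than 0.3 SD by chance. An unadjusted contrast carries r times that difference.

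**The case against.** The strongest reply is that the plan never says baseline is left out. The endpoints are called changes. Quality of life is analysed from each study visit, and screening is a numbered visit. Section 7.2 also defines evaluable sets by the presence of the necessary baseline and on-study measurements. A change-from-baseline or longitudinal model that includes screening is thus not ruled out. This stands. A reader might infer that the sponsor has decided to ignore the screening data; the text supports only that their role is unspecified. The silence still matters, because covariate adjustment is more precise than each of the other open readings except the common-baseline-mean model, which equals it.

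A reader might also infer that a fixed share of the variance, such as a quarter to a half, is being lost. The documents do not support any single figure: that range corresponds to an assumed r of 0.5 to 0.7, and under a change-score reading the loss at those values is 15% to 25%.

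Nor should the point be read as bias. Arms are randomized, so the unadjusted contrast is unbiased and its standard error already allows for chance imbalance.

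Finally, these are secondary outcomes with no stated power and no multiplicity adjustment. At one-sided 0.15 the illustrative gain is 6 to 11 percentage points, against 12 to 28 at two-sided 0.05. That tempers the importance. It does not argue against a change that costs nothing.

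**Conclusion.** The point holds as an improvement to the stated method. Section 7.2 names no baseline term for the key secondary models, although screening values are collected and the titer model uses them. Against a month-12 level comparison, adjustment removes r² of the contrast variance: 9% to 64% for r from 0.3 to 0.8. Against a change score it removes 35% to 10% over the same range. Both ranges rest on an assumed r, equal variances and complete data. The power figures further assume the effect size and, for these endpoints, the test level, and are illustrative only.

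One caveat on the data: screening collection of the 6-minute walk is implied by the general reference to physical function testing and is not itemized.

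The plan should make this change. It affects precision for secondary outcomes only and does not touch the primary analysis.

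**What to change.** Add one sentence to section 7.2: each key secondary model includes the screening value of that outcome as a covariate, with arm by discrete visit over all post-dose visits at which the outcome is measured, and the adjusted month-12 contrast of each dose against placebo is the main comparison.

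The visits are months 2, 6 and 12 for frailty and physical function. For the SF-36 they are all scheduled post-dose quality-of-life visits. That list needs settling, because Table S-1 marks quality of life in the month 3 to 5 and 7 to 11 columns while section 6.9 does not include it in the monthly phone visits. A model with a common baseline mean across arms would be an acceptable equivalent, with the same variance in the check above.

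Separately, sex is the randomization stratification factor (section 5.3) and could be added to these models at no cost. The titer model as described does not include it either, so this is a distinct recommendation.

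The cost is an edit to the text before unblinding. No new visits, measurements or subjects are needed.
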